5.7 Follow-up of Adverse Events

For this trial, information on all AEs will be followed for up to 30 (+ 3) days after the last dose of IMP has been administered.

Protocol 31-14-204

5.7.1 Follow-up of Nonserious Adverse Events

Nonserious AEs that are identified at any time during the trial must be recorded on the AE eSource with the current status (ongoing or resolved/recovered) noted. All nonserious events (that are not IREs) that are ongoing at the last scheduled contact will be recorded as ongoing on the eSource. For any AE having been identified throughout the trial, during analysis, additional relevant medical history information may be requested by the sponsor to further ascertain causality (including, but not limited to, information such as risk-related behavior, family history and occupation).

5.7.2 Follow-up of Serious Adverse Events and Immediately Reportable Events

This trial requires that subjects be actively monitored for SAEs up to 30 (+ 3) days after the last dose of IMP is administered.

Serious AEs and nonserious IREs that are **identified or ongoing at the last scheduled contact** must be recorded as such on the AE eSource page. If updated information (eg, resolved status) on SAE or IRE status becomes available after a subject's last scheduled contact (up to last in-clinic visit for the entire trial), this must be reported to the sponsor and recorded on the AE eSource, according to the appropriate reporting procedures. The investigator will follow SAEs until the events are resolved, stabilized, or the subject is lost to follow-up or has died. Resolution means that the subject has returned to the baseline state of health and stabilized means that the investigator does not expect any further improvement or worsening of the subject's condition. The investigator will continue to report any significant follow-up information to the sponsor up to the point the event has resolved or stabilized, or the subject is lost to follow-up or has died.

5.7.3 Follow-up and Reporting of Serious Adverse Events and Immediately Reportable Events Occurring after Last Scheduled Contact

Any new SAEs reported to the investigator which occur **after the last scheduled contact** and are determined by the investigator to be reasonably associated with the use of the IMP, should be reported to the sponsor. This may include SAEs or IREs that are captured on follow-up telephone contact or at any other time point after the defined trial period. The investigator should follow SAEs or IREs identified after the defined trial period and continue to report any significant follow-up information to the sponsor until the events are resolved or stabilized, or the subject is lost to follow-up or has died.

Protocol 31-14-204

6 Pharmacokinetic Analysis

No PK analysis is planned.

7 Statistical Analysis

7.1 Sample Size

The planned sample size for the double-blind randomized withdrawal phase is 114 subjects (ie, 38 subjects per treatment group). Assuming the proportion of randomized subjects experiencing relapse during the double-blind randomized withdrawal phase will be 65% in the placebo group and 34% in each of the 2 aripiprazole dose groups, 114 subjects will provide approximately 80% power to detect a hazard ratio of 0.4 for relapse (either aripiprazole dose group versus placebo) at the alpha level of 0.05 (2-sided). Under the above assumptions, a total of 51 relapse events are expected to be observed during the randomization phase. However, subject enrollment will stop when 51 relapse events have accrued or 114 subjects have been randomized, whichever occurs earlier.

The sample size will allow one IA at approximately 70% of events accrual time point. The O'Brien-Fleming boundaries were used for sample size calculation of the interim analysis so that the interim analysis will be conducted when 36 relapse events occur.¹⁹ The 2-sided alpha levels for the IA is 0.016, and the alpha left for the final analysis will be 0.045.

In order to randomize 114 subjects, approximately 228 subjects will need to enter the open-label stabilization phase of the trial, assuming that the stabilization rate is 50%.

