2.2 Dosing Rationale

Based on the approved labeling aripiprazole in the US for TD, the 5 to 20 mg once-daily tablets are expected to result in safe, tolerable, and efficacious aripiprazole concentrations.¹² The goal of this trial is obtain long-term efficacy, safety, and tolerability data in a controlled condition of a once-daily aripiprazole formulation in children and adolescents with TD. Additionally, this trial will evaluate if the long-term therapeutic benefit is maintained with a lower dose of aripiprazole.

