3.7 Trial Procedures

The duration of this trial from first subject enrolled to last subject completed is estimated to be approximately 3 years and 4 months including an estimated 30-month recruitment period.

Individual participation for subjects who complete the trial can range from a minimum of approximately 30 weeks to approximately 42 weeks. Length of participation will vary, depending on the screening duration (3 - 42 days).

Protocol 31-14-204

However, the trial may be terminated early based on the result of a planned interim analysis (IA).

During the open-label stabilization phase, visits will occur at Week 1 (± 2 days) for the titration visit and at Weeks 2, 3, and 4 (± 2 days) and Weeks 6, 8, 10, 12, 14, 16, 18, and 20 (± 3 days). Upon entering the double-blind randomized withdrawal phase, subjects will be randomized to aripiprazole full dose, aripiprazole half dose, or placebo. Subjects will have trial visits at Weeks 1, 2, 3, and 4 (± 2 days) and Weeks 6, 8, 10, and 12 (± 3 days).

Screening assessments may occur during 1 or more visits (as needed), and must occur in the clinic. The baseline visit will occur in the clinic, as well the open-label stabilization phase visits on Weeks 1, 2, 4, 8, 12, 14, 16, 18, and 20 and the double-blind, randomized withdrawal phase visits at Weeks 1, 2, 4, 8, and 12. All other visits will occur via telephone with direct patient visualization (except for open-label Week 3 which does not require direct patient visualization), web, in-clinic, or other acceptable means of contact. Trial assessment time points are summarized by phase in [Table 3.7-1](#) (Pretreatment and Open-label Stabilization Phase) and [Table 3.7-2](#) (Double-blind Randomized Withdrawal Phase).

Protocol 31-14-204

Assessments/Procedures	Screening and Washout Period (Days -42 to -3)	Open-label Stabilization Phase Visits - Week (Day) ^a												
		Baseline (Day 1)	1 (8 ± 2)	2 (15 ± 2)	3 (22 ± 2)	4 (29 ± 2)	6 (43 ± 3)	8 (57 ± 3)	10 (71 ± 3)	12 (85 ± 3)	14 (99 ± 3)	16 (113 ± 3)	18 (127 ± 3)	20 (141 ± 3) / EOP or ET ^b
Screening/Eligibility														
Informed Consent/Assent ^c	X													
Confirmation of diagnosis of TD by DSM-5 ^d	X													
K-SADS-PL ^e	X													
CY-BOCS ^f	X													
Inclusion/exclusion criteria	X	X												
Demography	X													
Medical history	X													
Psychiatric history	X													
Record current psychotropic therapy ^g	X	X	X	X		X	X	X	X	X	X	X	X	X

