3.8 Stopping Rules, Withdrawal Criteria, and Procedures

3.8.1 Entire Trial or Treatment Arm(s)

If the sponsor terminates or suspends the trial for any reason, prompt notification will be given to investigators, IRBs/IECs, and regulatory authorities in accordance with regulatory requirements. One IA is planned ([Section 7.4.4](#)) so that the trial can be terminated if the null hypothesis on the comparison between aripiprazole full dose and placebo is rejected at the IA time point.

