7.4 Primary and Secondary Endpoint Analyses

7.4.1 Primary Endpoint Analysis

The primary endpoint is time from randomization to relapse during the double-blind randomized withdrawal phase. Subjects who complete or discontinue from the randomization phase without relapses will be considered as censored observations. The primary objective of the trial is to evaluate the long-term efficacy of aripiprazole once-daily treatment in pediatric subjects with TD. This will be accomplished by comparing the long-term efficacy of aripiprazole full-dose and half-dose with that of placebo with regard to time to relapse. Hazard ratio and its 95% confidence interval (CI) will be estimated from the Cox proportional hazard model with treatment as a factor. The p-value from the log rank test will be presented to compare survival (subjects free of relapse) distributions, ie, Kaplan-Meier (KM) curves, between the treatment groups.

Analyses of the primary endpoint will use the data of subjects from the ITT Sample.

The statistical comparison will be performed by the log-rank test comparing each aripiprazole treatment groups with placebo at an overall nominal significance level of 0.05 (two-sided) following a group sequential procedure described as follows. One IA is planned at approximately 70% of events accrual time point using the O'Brien-Fleming boundaries for rejection of the null hypothesis, as detailed in [Table 7.4.1-1](#).

Protocol 31-14-204

Table 7.4.1-1 Boundaries for Rejection of Null Hypothesis for Interim and Final Analysis		
Analysis	Number of Events	Two-sides Alpha Level^a
Interim analysis (\approx 70%)	36	0.016
Final analysis (100%)	51	0.045

^aObtained using East 6.4 sample size software.

As there are 2 comparisons of the primary endpoint (one for aripiprazole full-dose vs placebo and the other for aripiprazole half-dose vs placebo), Type I error rate will be controlled for the primary endpoint at the alpha level specified in [Table 7.4.1-1](#) using a fixed sequence procedure in the order of the full-dose and then the half-dose comparisons. That is, one must reject the null hypothesis of the comparison of aripiprazole full-dose to placebo at the level of 0.016 for interim analysis and 0.045 for final analysis (two-sided) in order to proceed to test the hypothesis of the comparison of aripiprazole half-dose to placebo at the level of 0.016 for interim analysis and 0.045 for final analysis (two-sided).

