7.4.4 Interim Analysis

One IA is planned for the assessment of efficacy. The analysis will be performed following a group sequential approach at approximately 70% of events accrual time point and will include all randomized subjects. Subjects who withdraw early from the trial, or who are still in the trial at the end of trial without relapse, will be considered as censored observations. The O'Brien-Fleming boundaries will be used for the IA so that the IA will be conducted when 36 impending relapse events are available. The 2-sided alpha level for the IA is 0.016 and the alpha left for the final analysis will be 0.045 as specified in [Table 7.4.1-1](#). Additionally, a 95% CI for the hazard ratio (either aripiprazole or placebo) will be provided using the Cox proportional hazard model with term of treatment in the model.

If the null hypothesis on comparison between aripiprazole full dose and placebo is rejected at the IA time point, the trial will be terminated. An IA plan will be developed to document the details of the stopping rules, data flow and other logistical considerations relating to the IA.

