8.1 Primary Efficacy Endpoint

8.1.1 Primary Endpoint Analysis

The primary endpoint is time from randomization to relapse during the double-blind randomized withdrawal phase. Relapse is defined as a loss of $\geq 50\%$ of the improvement experienced during the open-label stabilization phase (i.e., improvement at the last

assessment of YGTSS before randomization) on the YGTSS TTS. Since this trial has terminated early due to withdrawal of postmarketing commitment (PMC), only relapse rate will be provided by treatment group for ITT sample.

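### The stated 80% power holds for full dose only; half-dose power under the fixed sequence is about 56% or 68%, depending on the interim rule, and is not stated

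*Protocol*

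**What the plan says.** Protocol 7.1 gives one power figure: "114 subjects will provide approximately 80% power to detect a hazard ratio of 0.4 for relapse (either aripiprazole dose group versus placebo" at two-sided 0.05. The synopsis and SAP 4 repeat it. The inputs are 38 subjects per arm, relapse of 65% on placebo and 34% on each aripiprazole dose, 51 events in total, and an interim at 36 events, with two-sided levels of 0.016 (interim) and 0.045 (final).

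Protocol 7.4.1 makes both dose comparisons part of the primary analysis but orders them. The full-dose null has to be rejected "in order to proceed to test the hypothesis of the comparison of aripiprazole half-dose to placebo at the level of 0.016 for interim analysis", and likewise at 0.045 at the final.

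The protocol describes what follows a full-dose rejection at the interim in two ways. Section 7.4.4 is mandatory and sets no condition on the half-dose result: "If the null hypothesis on comparison between aripiprazole full dose and placebo is rejected at the IA time point, the trial will be terminated". Section 3.8.1 is permissive: the interim is planned "so that the trial can be terminated if the null hypothesis on the comparison between aripiprazole full dose and placebo is rejected". Section 7.4.4 leaves the detail to a separate document: "An IA plan will be developed to document the details of the stopping rules, data flow and other logistical considerations relating to the IA".

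Protocol 2.2 gives the lower dose its own purpose: "this trial will evaluate if the long-term therapeutic benefit is maintained with a lower dose of aripiprazole".

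Neither document states the power for half dose under these rules, or says that the 80% applies before the testing order is taken into account.

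**The concern.** The power sentence treats the two doses alike, but the testing procedure does not. The second hypothesis in a fixed sequence can be claimed only when the first is also rejected, so its power is a joint probability and lies below its stand-alone power. If the trial also ends when the first hypothesis succeeds at the interim, the second has to succeed at that look, on 36 events and at 0.016.

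Half dose versus placebo is one of two primary comparisons, and the only one that bears on whether benefit is maintained at a lower dose. A reader of the sample-size sections alone could credit it with about 80% power and read a non-significant half-dose result accordingly.

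**Working it through.** **Inputs.** From Protocol 7.1 and 7.4.1: 38 per arm, relapse 65% / 34% / 34%, hazard ratio 0.4, looks at 36 and 51 events, two-sided levels 0.016 and 0.045, full dose before half dose. My assumptions: no dropout in the randomized phase (the documents give no rate), and a correlation of 0.5 between the two comparisons, which follows from a shared placebo arm at 1:1:1.

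**Step 1: reproduce the stated figure.**
- Total events: 38 × (0.65 + 0.34 + 0.34) = 50.5, agreeing with 51.
- Events in one pairwise comparison: 38 × (0.65 + 0.34) = 37.62.
- Expected log-rank statistic (Schoenfeld): −ln(0.4) × √(37.62/4) = 0.916 × 3.067 = 2.810.
- Power at two-sided 0.05: Φ(2.810 − 1.960) = Φ(0.850) = 80.2%.

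The 80% is the power of one comparison. Power to win on at least one dose would be about 91%, so the stated figure cannot be that.

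**Step 2: full dose with the interim.**
- Information fraction: 36/51 = 0.706. Expected statistic at the interim: 2.810 × √0.706 = 2.361.
- Critical value at 0.016: 2.409. P(full dose rejected at interim) = Φ(2.361 − 2.409) = 48.1%.
- Over both looks: 79.6%. The two levels together spend a two-sided alpha of 0.0500.

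**Step 3: half dose under the sequence.** Joint normal model for the four statistics (two doses, two looks), 2 million draws. With termination, half dose is claimed if both doses pass 0.016 at the interim, or if full dose fails at the interim and both pass 0.045 at the final.
- Claimed at the interim: given a full-dose rejection there, half dose also passes 0.016 in 65.4% of cases, so 0.481 × 0.654 = 31.5%.
- Claimed at the final: 56.4% − 31.5% = 24.9%.
- Trial ended with half dose short of 0.016: 48.1% − 31.5% = 16.6%.

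With continuation, half dose can also pass 0.045 at the final after a full-dose rejection at the interim.

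| Quantity | Corr. 0.4 | Corr. 0.5 | Corr. 0.6 |
|---|---|---|---|
| Full dose | 79.6% | 79.6% | 79.6% |
| Half dose, trial ends at interim on full-dose rejection | 54.5% | 56.4% | 58.6% |
| Half dose, trial continues to final | 67.0% | 68.1% | 69.3% |

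At correlation 0.5 the testing order costs 79.6 − 68.1 = 11.5 points, and termination a further 68.1 − 56.4 = 11.7.

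**Step 4: checks.**
- Subject-level log-rank simulation with exponential relapse times and 12-week censoring (20,000 trials): full dose 79.1%, half dose 56.2% with termination and 67.8% with continuation. The simulated correlation was 0.51.
- Cutting the final data at the 51st event gives 53.7% with termination, and adding 10% dropout gives about 53%.
- Using the hazard ratio implied by the relapse rates, ln(0.66)/ln(0.35) = 0.396, gives 57.5% with termination.

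**The case against.** The strongest reply is that no figure is wrong. The sentence gives a pairwise power, the pairwise power is right, and Protocol 7.4.1 and 7.4.4 disclose the order and the interim rule. Sizing a fixed sequence on the pairwise comparison and accepting less for the second step is common practice. Much of this stands: a reader might infer an arithmetic error or a trial that is too small, and the documents support neither. The number of subjects, the event count, the alpha levels and full-dose power agree with one another. What remains is that a single figure is offered for both doses when the procedure delivers it for only one.

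A second reply is that 56% should not be read as the plan's own figure. That stands too. It depends on taking the mandatory wording of 7.4.4 over the permissive wording of 3.8.1, on no dropout, and on half dose being judged on interim data alone. The interim analysis plan that would settle this is not among the documents. A retest of half dose on events after the interim might also be imagined, but neither document provides for one, so I give no figure for it.

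A third reply is that nothing now turns on this. SAP 8.1.1 says that "only relapse rate will be provided by treatment group for ITT sample", and SAP 13 and 14 drop the interim and make efficacy descriptive. This is correct and sets the severity.

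**Conclusion.** The concern holds as a misattributed power statement. About 80% is the marginal power of one comparison and the power for full dose. Under either reading of the interim rule, half dose falls short of it: by about 23 points with termination (79.6 − 56.4) and about 12 with continuation (79.6 − 68.1). These sizes rest on the protocol's equal-effect assumption for the two doses, a hazard ratio of 0.4, looks at 36 and 51 events, no dropout, and a correlation near 0.5. I am confident that half-dose power is below 80% and is unstated; which of the two figures applies cannot be settled from the documents. Severity is minor, because the reported analysis contains no hypothesis test and no result changes.

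**What to change.** 1. Reconcile Protocol 3.8.1 and 7.4.4 on whether a full-dose rejection at the interim ends the trial or merely permits ending it.
2. In Protocol 7.1, the synopsis and SAP 4, reword the power statement so that about 80% refers to full dose versus placebo, and to each comparison taken alone before the testing order applies.
3. In the same places, state half-dose power under the fixed sequence and the reconciled interim rule, with its assumptions: about 56% with termination or about 68% with continuation, confirmed in the sponsor's own design software.
4. In SAP 4, add that the power statement describes the protocol's design and does not apply to the descriptive analysis in SAP 8.1.1 and 14.

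The cost is one qualifying sentence in three places, one wording alignment and one cross-reference. As the trial has terminated, the SAP 4 note is the part with practical use; a protocol edit would go through the amendment policy in Protocol section 13.

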7.2 Datasets for Analysis

The following analysis datasets are defined for this trial:

- Open-label Safety Sample: The Open-label Safety Sample includes all subjects that are administered at least one dose of IMP during the open-label stabilization phase.
- Intent to treat (ITT) Sample: All subjects who are randomized and receive at least one dose of randomized IMP will be included in this dataset and analyzed according to the treatment group they are randomized to. The ITT Sample will serve as the primary efficacy dataset for all efficacy endpoints in the double-blind randomized withdrawal phase.

Protocol 31-14-204

- **Randomized Safety Sample:** All subjects who receive at least one dose of randomized IMP during the double-blind randomized withdrawal phase will be included and analyzed according to the treatment actually received.

7.3 Handling of Missing Data

The primary endpoint is time from randomization to relapse during the double-blind randomized withdrawal phase. Subjects who complete or discontinue from the randomization phase without relapses will be considered as non-informative censoring in the primary analysis of the primary endpoint. Non-informative censoring means the dropout reason for subject who drops out of the trial without relapse is unrelated to efficacy. However, as the possibility of potential informative censoring in the randomized phase cannot be ruled out, sensitivity analyses of the primary endpoint will be performed under the assumption of informative censoring. Details of such sensitivity analyses will be provided in the statistical analysis plan (SAP).

7.4 Primary and Secondary Endpoint Analyses

7.4.1 Primary Endpoint Analysis

The primary endpoint is time from randomization to relapse during the double-blind randomized withdrawal phase. Subjects who complete or discontinue from the randomization phase without relapses will be considered as censored observations. The primary objective of the trial is to evaluate the long-term efficacy of aripiprazole once-daily treatment in pediatric subjects with TD. This will be accomplished by comparing the long-term efficacy of aripiprazole full-dose and half-dose with that of placebo with regard to time to relapse. Hazard ratio and its 95% confidence interval (CI) will be estimated from the Cox proportional hazard model with treatment as a factor. The p-value from the log rank test will be presented to compare survival (subjects free of relapse) distributions, ie, Kaplan-Meier (KM) curves, between the treatment groups.

Analyses of the primary endpoint will use the data of subjects from the ITT Sample.

The statistical comparison will be performed by the log-rank test comparing each aripiprazole treatment groups with placebo at an overall nominal significance level of 0.05 (two-sided) following a group sequential procedure described as follows. One IA is planned at approximately 70% of events accrual time point using the O'Brien-Fleming boundaries for rejection of the null hypothesis, as detailed in [Table 7.4.1-1](#).

Protocol 31-14-204

Table 7.4.1-1 Boundaries for Rejection of Null Hypothesis for Interim and Final Analysis		
Analysis	Number of Events	Two-sides Alpha Level^a
Interim analysis (\approx 70%)	36	0.016
Final analysis (100%)	51	0.045

^aObtained using East 6.4 sample size software.

As there are 2 comparisons of the primary endpoint (one for aripiprazole full-dose vs placebo and the other for aripiprazole half-dose vs placebo), Type I error rate will be controlled for the primary endpoint at the alpha level specified in [Table 7.4.1-1](#) using a fixed sequence procedure in the order of the full-dose and then the half-dose comparisons. That is, one must reject the null hypothesis of the comparison of aripiprazole full-dose to placebo at the level of 0.016 for interim analysis and 0.045 for final analysis (two-sided) in order to proceed to test the hypothesis of the comparison of aripiprazole half-dose to placebo at the level of 0.016 for interim analysis and 0.045 for final analysis (two-sided).

As a secondary analysis of the primary endpoint, the proportion of subjects experiencing relapse during the double-blind randomized withdrawal phase will be compared between each of the aripiprazole dose groups to placebo. The proportion of relapsed subjects will be computed as 1 minus the KM estimate of the proportions of subjects free of relapses during the double-blind randomized withdrawal phase. Group difference in the proportion of relapsed subjects will be tested using 2-sided Z test with standard error computed from the Greenwood formula. Point estimate of the group difference and its 95% CI will also be provided

Sensitivity analyses will be conducted to assess the sensitivity of the primary efficacy analysis results to the potential informative censoring which will be detailed in the SAP.

Subgroup analyses may be conducted for the primary endpoint based on subject baseline YGTSS TTS score, sex, and age if specific subgroups have reasonable sample sizes to permit such analyses.

